	
two-sided alpha level of 5%, the total sample size of 336 gives 80% power to detect a 4–point difference between the two groups, after allowance for 15% dropouts. This effect size is estimated to represent a 25% reduction in the rate of worsening after allowance for the benefit of symptomatic treatment. Secondary outcomes including measures of motor, cognitive and global disability and measures of functional changes and quality of life will be analyzed in the same way as the primary outcome. Measures of safety and tolerability, including ability to complete the study on the assigned dosage and the frequency, seriousness and severity of adverse events will be compared using Fisher’s exact test.

Interim Analyses	
Interim tolerability analysis
 
An interim tolerability analysis will be performed after the first 60 subjects complete the titration period (Visit 03, Month 3).
 
Interim analysis of the Pharmacokinetic (PK) data
 
An interim PK data analysis will be performed (at steady-state) after Cmin and Cmax PK data are available for the first 60 subjects who successfully complete titration to the target daily dose of 10 mg (Visit 03, Month 3).
 
Interim futility and efficacy analysis
 
An interim analysis for futility and efficacy will be performed after primary outcome data are available for the first 168 subjects (50%) to enroll in the study. If the recruitment rate falls below that projected, the interim analysis may be brought forward and performed as soon as the first 30% of the subjects to enroll have completed (or terminated). In that case, a second interim analysis for futility will be conducted on the first 75% of subjects to enroll.

Study Procedures	See the Schedule of Activities.
IND	The IND application # 113,513

STEADY-PD III Schedule of Activities

		Titration Phase				Maintenance Phase										Drug Taper					
Visits	Screen (SC)	Baseline (BL)	V01	V02	V03	V04	V05	V06	Phone Visit T01	V07	Phone Visit T02	V08	Phone Visit T03	V09	Phone Visit T04	V10 EOS D	V11 Post drug/ Final Visit	Premature Withdrawal (PW)	PW Follow-Up Visit ¹¹	Unscheduled Visit (U01, U02) ⁵	Symptomatic Tx Visit

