8.2.2. Secondary Outcomes

Efficacy analysis (at 36 months):

The change in the following measures of disability from baseline to 36 months will be analyzed:

- I. Motor disability
 - a. The change in UPDRS Part III Motor subscale in the defined medications OFF state (approximately 12 hours after the last dose of symptomatic therapy for those subjects that have initiated symptomatic therapy)
 - b. MDS-UPDRS Motor score in the defined medications ON state (as per the primary outcome)
 - c. The change in the ambulatory capacity (sum of 5 UPDRS questions: falling, freezing, walking, gait, postural stability)
 - d. Time to initiation of symptomatic therapy
 - e. Proportion of subjects that start symptomatic therapy
 - f. Analysis of symptomatic therapy utilization as measured by levodopa equivalence dose[1]
 - g. Time to onset and severity of motor complications as measured by UPDRS IV subscale (complications of therapy) for those subjects that have initiated symptomatic therapy

For continuous measures, the analysis will proceed in the same way as for the primary outcome measure. Logistic regression will be used for the binary out-

come (e) and Cox's proportional hazards model for the time-to-event outcomes (d) and (g).

II. Cognitive disability

a. The change in the cognitive function as measured by the change in the MoCA [2, 3]

III. Measure of global disability

a. The change in the Modified Rankin score

IV. Measures of functional status and quality of life

a. The change in Activities of Daily Living (ADL) subscale of the UPDRS

b. The change in the MDS-UPDRS Part II

c. The change in the modified Schwab and England scale

d. The change in Parkinson Disease Quality of Life Questionnaire-39 (PDQ-39) [4]

e. The change in Neuro-QOL

f. The change in Non-motor and Motor Experiences of Daily Living scores of the MDS-UPDRS

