A. *Intent-to-Treat.* Efficacy analyses will use the intent-to-treat principle, whereby all subjects are kept in their assigned treatment groups for statistical analysis, even if they discontinue study medication or continue on a reduced dosage. Subjects who discontinue study medication will be encouraged to remain in the study and their data will be used in the primary efficacy analysis. Subjects who have no post-baseline efficacy data will be excluded from the primary analysis as their primary outcome variable will be missing. The primary analysis will compare the active treatment group (all subjects randomized to receive active isradipine) to the placebo group. All P-values for efficacy outcomes will be two-sided.

B. *Baseline Characteristics.* Demographic and clinical characteristics, including age, gender, race and ethnicity, years of education, time since PD diagnosis, UPDRS score at entry including its mental, motor and ADL components, MDS-UPDRS, Modified Rankin Score, Modified Hoehn and Yahr score, PDQ-39 score, MOCA score (adjusted for education level) of the two treatment groups will be presented. Systolic and Diastolic blood pressure and other vital signs data will also be shown.

C. *Subject Disposition.* Losses to follow-up, compliance to study medication, protocol violations and other notifiable incidents will be tabulated. A CONSORT type diagram showing the progress of all enrolled subjects through the study will be prepared.

(Numbers of subjects screened but ineligible, and those eligible but not enrolled, will be provided by the CTCC).

3. Primary Efficacy Analysis

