A. Outcome Variable. The pre-specified primary outcome variable will be the change from baseline to the three-year follow-up visit in the total score from Parts I, II and III of the UPDRS score (mental, motor and ADL components). We anticipate that by the three year visit a substantial majority of participants will be receiving symptomatic medication. Unlike in previous studies in early PD (e.g. DATATOP, PRECEPT, QE3)[1-3] subjects who require symptomatic treatment (typically levodopa or dopamine agonists) during the course of the study will continue in the study, receiving their assigned study medication. By this strategy we hope to minimize drop-outs. For subjects receiving symptomatic medication the UPDRS will be assessed in the ON state, based on the subject/ investigator defined BEST ON, approximately 1 hour after dose of symptomatic therapy). Subjects who do not complete the three-year visit will have their primary outcome variable set to missing; a variety of sensitivity analyses (see below) will be conducted to assess the influence of these subjects on the primary analysis.

B. Statistical Model. The primary analysis will use analysis of covariance applied to the change from baseline in the total UPDRS score. The baseline value will also be entered into the model as a continuous variable, the assigned treatment and enrolling site will be entered as categorical variables. A two-tailed test with $\alpha = 0.05$ will be used to declare statistical significance.

C. Adjustments to the Analysis. (i) It may occasionally happen that certain items on the UPDRS are missing at a particular visit, for example if a subject is unable to perform a test due to injury. To enable the valid data from that visit for that subject to be used in the analysis, single missing items on the UPDRS will be carried forward from the subject's previous visit. A maximum of five missing items may be carried forward in this way, including from the baseline visit to the one-month visit if necessary. Items missing at baseline may be carried forward from the screening visit. (ii) For analyses that include the enrolling site as a stratification factor, sites that enroll fewer than four subjects will be combined to form a single "super-site".

4. Secondary Efficacy Analyses

A. 36-month data. The changes from baseline to 36 months in the following measures of disability will be analyzed in a similar fashion as that for the primary outcome variable

I. Motor disability

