- a. The change in UPDRS Part III Motor subscale in the defined medications OFF state (approximately 12 hours after the last dose of symptomatic therapy for those subjects that have initiated symptomatic therapy)

- b. MDS-UPDRS Motor score in the defined medications ON state (as per the primary outcome)
 - c. The change in the ambulatory capacity (sum of 5 UPDRS questions: falling, freezing, walking, gait, postural stability)
 - d. Proportion of subjects receiving symptomatic therapy
 - e. Current usage of symptomatic therapy utilization as measured by levodopa equivalence dose[4]
 - f. Prevalence of motor complications as measured by UPDRS IV subscale (complications of therapy) for those subjects that have initiated symptomatic therapy
- II. Cognitive disability
- a. The change in the cognitive function as measured by the change in the MoCA [5, 6]
- III. Measure of global disability
- a. The change in the Modified Rankin score
- IV. Measures of functional status and quality of life
- a. The change in Activities of Daily Living (ADL) subscale of the UPDRS
 - b. The change in Non-motor and Motor Experiences of Daily Living scores of the MDS-UPDRS (Part I and II)
 - c. The change in the modified Schwab and England scale
 - d. The change in Parkinson Disease Quality of Life Questionnaire-39 (PDQ-39) [7]

B. Longitudinal Analyses. Outcome data from all subject visits will be plotted over time by treatment group.

I. Time-dependent events

Kaplan-Meier plots and Cox regression will be used to analyze the following events:

- a. Time to initiation of symptomatic therapy
- b. Time to complications of symptomatic therapy, including wearing-off, dyskinesias and sudden “on-offs”.

II. Early Effects:

- a. Plots of the mean and standard error of the total UPDRS and related outcome variables will be constructed.
- b. Changes in total UPDRS from baseline to the one year visit or to the initiation of symptomatic therapy between treatment groups will be compared using analysis of covariance (as for the three-year analysis).
- c. Changes in total UPDRS following the introduction of symptomatic therapy will be compared between treatment groups in the same way.
- d. Multiple regression analysis and other techniques as appropriate will be used to examine whether early outcomes (e.g. short-term changes in UPDRS, time to initiation of symptomatic therapy) are useful predictors of long-term disability.

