The key issues in the determination of sample size are the variability of the primary outcome measure and the magnitude of the treatment effect one wishes to detect.

As regards the former, there are several sources of data regarding changes in total UPDRS in untreated patients to a two, three or four year point, generally following introduction of symptomatic therapy. Published sources include the CALM-PD study [8] and the Swedish selegiline study [9]. Unpublished data are also available from a long-

term follow-up of patients originally enrolled in the PRECEPT study [2]. All these studies support a standard deviation of 12.0 units for the change in total UPDRS from baseline to 36 months. The same data suggest an average change in total UPDRS of around 4.0 points over this same time period. Of course this change is deceiving, as the change would likely be much greater in the absence of symptomatic treatment. If we assume that treatment with levodopa or a dopaminergic agonist provides a “bonus” of 12 points, then the underlying true decline in function over this period would be around 16 points, a value broadly consistent with the rate of change in total UPDRS in subjects prior to treatment. We have chosen to power our study to detect a four point effect, representing an overall 25% reduction in the underlying rate of progression. We believe that a difference of this magnitude would be sufficient to influence clinical practice and may suggest the likelihood of longer term benefit.

Using the above assumptions, a two-sided test with $\alpha = 0.05$ and $\beta = 0.8$ and making allowance for 15% dropouts the required sample size is 168 subjects per group or a total 336 subjects.

The Table below shows the effect of higher than expected withdrawal rates (20% and 25%) expressed in three alternative metrics (A) The power to detect a 4.0 point difference, (B) The effect size that would be detectable with 80% power and (C) the number of additional subjects that would need to be enrolled to maintain power at 80% to detect a 4.0 point difference.

| Overall Withdrawal Rate | Power (A) | Effect Size (B) | Additional Subjects (C) |
|-------------------------|-----------|-----------------|-------------------------|
| 15% | 80% | 4.0 pts. | 0 |
| 20% | 78% | 4.1 pts | 21 |
| 25% | 75% | 4.25 pts. | 45 |

Power for key secondary outcomes

We will also examine power for some key secondary outcomes of this study.

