Time to Initiation of Symptomatic Therapy. After allowing for 15% dropouts, half of these prior to need for symptomatic therapy, and 10% of subjects not requiring symptomatic treatment three years after enrollment, we estimate that approximately 275 subjects will have reached this milestone by the conclusion of the study. By the formula of George and Desu[10], this translates to a detectable hazard ratio of 0.71, i.e. a 29% reduction in the risk of reaching this milestone per unit of time.

Rationale for the selection of this secondary outcome:

Time to initiation of symptomatic therapy has been a primary outcome in a number of previously completed studies that examined the efficacy of putative disease modifying interventions[2, 3, 11]. While it has been criticized for the subjective nature of the measure and being impacted by the change in the treatment algorithms that overall lead to the earlier initiation of symptomatic therapy, nevertheless it can be considered a surrogate measure of the disease progression and as such should be considered as a key secondary outcome.

Complications of Therapy. In the CALM-PD study approximately 40% of subjects enrolled experienced complications of therapy within two years of follow-up. Since subjects in CALM-PD were enrolled at the time they needed therapy, the experience of our subjects after three years of follow-up is expected to be similar. A total of 120 subjects reaching this milestone gives a detectable hazard ratio of 0.60, i.e., a reduction of 40% in the risk per unit of time. For the purpose of this analysis complications of therapy will be measured by UPDRS IV subscale (complications of therapy) for those subjects that have initiated symptomatic therapy

Rationale for the selection of this secondary outcome:

Time to onset of motor complications is considered an important milestone in the disease progression signifying transition from early to more advanced disease and has been used as a primary outcome in a number of previously completed studies[12-14] . A disease modifying intervention that shows an impact on this milestone will have a meaningful impact on the progression of disability and as such should be considered as a key secondary outcome.

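### The Cox models for the two key time-to-event secondaries name no covariate; adding baseline total UPDRS would be a free, minor gain in efficiency

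*SAP*

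**What the plan says.** SAP section 4.B.I lists two events, the start of symptomatic therapy and complications of that therapy, and says that "Kaplan-Meier plots and Cox regression will be used to analyze the following events". It names no covariate or stratum. Protocol section 8.2.2 assigns logistic regression to the binary outcome and a Cox "proportional hazards model for the time-to-event outcomes (d) and (g"), again without covariates.

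The primary model is fuller. SAP section 3.B specifies analysis of covariance on the change in total UPDRS, with treatment and site as categorical terms, and adds: "The baseline value will also be entered into the model as a continuous variable". How far that model carries over to the secondaries is stated in two ways:

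- Protocol 8.2.2 restricts it: "For continuous measures, the analysis will proceed in the same way as for the primary outcome measure".
- The protocol synopsis is broader. After describing a primary analysis adjusted for baseline UPDRS and enrolling investigator, it says that secondary outcomes, including motor measures and "quality of life will be analyzed in the same way as the primary outcome".

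SAP section 7 treats both time-to-event outcomes as key secondaries. For the first, with about 275 events, it says "this translates to a detectable hazard ratio of 0.71, i.e. a 29% reduction in the risk of reaching this milestone per unit of time". For complications it gives 0.60 with 120 events. SAP section 2.A adds that "All P-values for efficacy outcomes will be two-sided".

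**The concern.** Leaving a prognostic covariate out of a Cox model moves the estimated treatment hazard ratio toward 1, even when the arms are balanced on it, and lowers power relative to the adjusted model.

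The documents make baseline UPDRS a plausible predictor here. Protocol section 6.3.12 bases the need for therapy on disability, including activities of daily living. UPDRS Part II measures those activities, and it is scored at the Baseline visit.

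Read most directly, 8.2.2 and 4.B.I describe an unadjusted model, so the plan may be passing up power that it could have without new data. The outcome matters: the SAP notes that time to symptomatic therapy was the primary outcome of earlier trials of disease modification. The December 2018 SAP clarification settled small sites and the levodopa-equivalent analysis but did not address this point.

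**Working it through.** **1. Reproduce the SAP's figures.** Inputs from SAP section 7: 336 subjects in two equal groups, two-sided alpha 0.05, 80% power (printed as beta = 0.8), 275 and 120 events. With an events formula that has no covariates, the detectable hazard ratio is exp(−2 × (1.960 + 0.842) / √events).

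- 275 events: exp(−5.604 / 16.58) = 0.713 (stated 0.71). Power at exactly 0.71 is 81.1%.
- 120 events: exp(−5.604 / 10.95) = 0.600 (stated 0.60). Power at exactly 0.60 is 79.9%.

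The event count is also consistent with the stated inputs (15% dropout, half of it before the event; 10% event-free at three years): 336 × (1 − 0.075 − 0.10) = 277, or 336 × 0.925 × 0.90 = 280, against about 275 stated.

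**2. Compare unadjusted with adjusted Cox.** The missing input is the hazard ratio per SD of baseline total UPDRS. It is an assumption here, varied from 1.0 to 2.0. For scale, the phase II trial in Protocol section 2.6 had a baseline SD of 9.9. The per-point equivalents are 1.25^(1/9.9) = 1.023, 1.5^(1/9.9) = 1.042 and 2.0^(1/9.9) = 1.073.

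Simulation: 336 subjects, 1:1, exponential event times, a standard normal baseline covariate, censoring at 36 months, about 15% dropout, and a baseline hazard tuned to the planned number of events. There were 2,000 trials per setting. The true hazard ratio is conditional on baseline. Power counts two-sided significance in favor of isradipine.

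| True HR, events | Assumed HR per SD | Unadjusted: HR, power | Adjusted: HR, power | Gain (points) |
|---|---|---|---|---|
| 0.71, 275 | 1.0 | 0.71, 80.1% | 0.71, 80.4% | 0.3 |
| 0.71, 275 | 1.25 | 0.71, 80.1% | 0.71, 82.1% | 2.0 |
| 0.71, 275 | 1.5 | 0.73, 74.8% | 0.71, 82.6% | 7.8 |
| 0.71, 275 | 2.0 | 0.76, 62.5% | 0.71, 79.7% | 17.2 |
| 0.60, 120 | 1.0 | 0.60, 78.1% | 0.60, 77.7% | −0.4 |
| 0.60, 120 | 1.25 | 0.60, 78.7% | 0.60, 79.6% | 0.9 |
| 0.60, 120 | 1.5 | 0.61, 76.0% | 0.60, 79.2% | 3.2 |
| 0.60, 120 | 2.0 | 0.63, 69.5% | 0.60, 78.9% | 9.4 |

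Monte Carlo error on each power figure is about 1 point, so the differences at 1.0 are noise and those at 1.25 are small.

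**3. Vary the event pattern for the first outcome.** With half the subjects starting therapy by 12 months (800 trials per setting), power is 77% versus 79% at 1.25, 72% versus 77% at 1.5, and 57% versus 76% at 2.0. The pattern is the same, with gains of 2 to 19 points.

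**The case against.** A reader might infer several stronger claims that the documents do not support.

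*That the plan decided to exclude baseline UPDRS.* It is silent. SAP section 1.C says the detailed plan will be completed later and that only its main features are given. The synopsis can be read as carrying the primary covariates into the secondaries. Section 8.2.2 points the other way, so the covariate set is open.

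*That every other efficacy model adjusts for baseline UPDRS.* The logistic regression in 8.2.2 names no covariate. MoCA, Rankin and PDQ-39 would most naturally use their own baseline values. Levodopa equivalent dose has no obvious baseline value in subjects who enter without dopaminergic therapy.

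*That power is certainly lost, or that the SAP's power statement is wrong.* The loss depends on an assumed prognostic strength and is close to nil at 1.25 per SD or below. Entry criteria narrow the baseline range (Hoehn and Yahr 2 or less, diagnosis under three years, no therapy expected for three months). The SAP itself calls the start of therapy subjective. Its formula has no covariates, so if 0.71 and 0.60 are read as unadjusted hazard ratios, the planned power stands and adjustment is purely a gain. The unadjusted test keeps its type I error and estimates a valid marginal effect.

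*That site strata should be ruled out.* With 336 / 56 = 6 subjects per site, stratifying costs information. But Protocol section 4.3.2.1 blocks randomization by site, which argues for reflecting site in the analysis. That trade-off is not settled here.

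All of these limits stand. What remains is that adjustment is harmless if baseline UPDRS is not prognostic and helpful if it is. The objectives are described as exploratory, and the primary conclusion is unaffected, which keeps the severity low.

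**Conclusion.** The point holds as a free improvement of minor severity. Neither document names a covariate for the two Cox models. Both stated detectable hazard ratios are correct for an unadjusted analysis.

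If the stated hazard ratios are conditional on baseline, the gain from adjustment runs from nothing to about 17 power points for symptomatic therapy, and from nothing to about 9 for complications. This covers assumed hazard ratios per SD from 1.0 to 2.0, and the documents do not say where in that range the truth lies. The figures also assume proportional hazards and the SAP's planned event counts.

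**What to change.** Before unblinding, add to SAP section 4.B.I and Protocol section 8.2.2: *Cox models will include treatment and baseline total UPDRS (continuous).* State that the resulting hazard ratio is conditional on baseline, and keep the Kaplan-Meier curves unadjusted as planned.

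The cost is one sentence in each document, with no new data, visits or subjects. The power statements in SAP section 7 can stay as they are.

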A pilot phase II double-blind, placebo-controlled, tolerability and dosage finding study of Isradipine CR as a disease modifying agent in patients with early Parkinson Disease (STEADY-PD) [36]. The objective of the study was to establish safety and tolerability of Isradipine CR across the FDA approved dosing range (5-20mg) in a larger cohort of patients with early PD and to evaluate comparative efficacy of three dosages of Isradipine CR provided that they are tolerable. The study recruited subjects with early PD not requiring dopaminergic therapy (stable dose of amantadine, anticholinergics and MAO-B inhibitors are allowed). The study was a multicenter 52 weeks, randomized, 4-arm double-blind parallel group trial with 100 subjects randomized to 5 mg, 10 or 20 mg of Isradipine CR or matching placebo daily. The dosage that was most tolerable and demonstrated preliminary efficacy was to be used in the proposed pivotal efficacy study. Tolerability of each active dosage was compared with the tolerability of placebo. Tolerability threshold was defined as more than 30% difference in the tolerability of each active treatment group relative to placebo. Provided that the dosage was tolerable, the choice for the dosage selection was to be based on efficacy defined as the change in total UPDRS score between the baseline visit and month 12 or the time of sufficient disability to require dopaminergic therapy (last visit before subject goes on dopaminergic therapy), whichever occurred first. *Comparison was made between three active treatment arms.* Power calculations for comparative efficacy analysis were made based on three point difference in total UPDRS between the active treatment groups. The dosage that demonstrated the greatest efficacy would be selected for the pivotal study. The study included a prespecified interim analysis for tolerability after 50 subjects had completed 12 weeks of the study.

Between September 2009 and October 2010, 115 subjects were screened and 99 enrolled in the study. There were 69 males, 30 females, predominantly White non-Hispanic, mean age at entry 59 (SD 9.77) years, average 0.95 (\pm 0.92) years from diagnosis, with no imbalances among treatment groups. Mean total UPDRS (Part I-III) at entry was 25.02 (\pm 9.9), with no significance imbalances. Compliance with the treatment was excellent (99.94% (SD 0.43) based on the pill count.

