C. *Sensitivity Analyses.* A variety of sensitivity analyses will be conducted to assess the robustness of the comparison between treatment groups.

- I. Non-parametric methods. Residual plots will be examined. In the event that these show outliers or pronounced non-normality, supplementary analyses will be performed after deletion of outliers and/or using appropriate non-parametric methods.
- II. Missing Data. Effects of missing data will be assessed (i) by multiple imputation and (ii) by “best case” and “worst-case” analysis and (iii) by the use of mixed models (which use intermediate study data to project final study outcomes when these are missing).
- III. Influence of Symptomatic Medication. Supplementary analyses of the final study outcomes will be conducted with current use of symptomatic medication (levodopa equivalents) added as an additional predictor variable. The purpose of this analysis is to assess whether any differences seen in the primary outcome variable could be attributed to differential use of symptomatic therapy between the treatment groups.

D. *Subgroup Analyses – Including Gender and Race/ Ethnicity*

Recognizing that the study will not have high power to detect treatment effects among subgroups, we will conduct exploratory analyses to check the consistency of treatment effects on the primary and secondary efficacy measures in relation to selected baseline characteristics, including gender and race/ ethnicity. The analysis will use two approaches (i) repeating the primary analysis for each subgroup (for example men and women; minority and non-minority) separately, (ii) inclusion of additional terms in the analysis of covariance model to represent the overall effect of the characteristic (do men progress faster than women?) and for the interaction of the treatment with the characteristic (does the effect of the treatment differ between men and women?). Results for each race/ethnic grouping will be tabulated separately.

5. Safety and Tolerability Analysis

A. *Primary Safety and Tolerability Outcomes.*

- I. The ability to complete the 36 months study on the originally assigned treatment dosage
- II. The proportion of subjects requiring dosage reductions secondary to intolerability
- III. The frequency of adverse events and serious adverse events
- IV. Laboratory and EKG abnormalities

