- (1) *Combining sites with low enrollment.* The SAP, section 3.C. states that for analyses that use sites as a stratification factor, sites with enrolling fewer than four subjects will be combined to form a single “super-site”. The sites affected are 016 (Ottawa) three subjects, 030 (Calgary) two subjects, 034 (IND) three subjects, 069 (PMDI), three subjects, 110 (UC Irvine), three subjects, 132 (LSU) three subjects, 139 (PHREI), two subjects, 305 (Alberta) three subjects, making a grand total of 22 subjects.

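### Refitting the primary ANCOVA, site factor included, inside small subgroups discards treatment information that the planned interaction model would keep

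*SAP*

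**What the plan says.** SAP 4.D gives two approaches to subgroups. The first is "i) repeating the primary analysis for each subgroup (for example men and women; minority and non-minority) separately". The second adds terms to the ANCOVA for the characteristic and for its interaction with treatment. The section calls the work exploratory, concedes that power is not high, and says that results for each race/ethnic grouping will be tabulated separately.

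The model to be repeated is in SAP 3.B: ANCOVA of change in total UPDRS with baseline as a continuous covariate and with treatment and enrolling site as categorical terms. SAP 3.C is the only relief from small sites: "sites that enroll fewer than four subjects will be combined to form a single" super-site. Item (1) of the December 2018 clarification applies that rule by total enrolment and lists the eight sites affected, "making a grand total of 22 subjects". Neither text says that pooling is redone, or that site is dropped, when the model is fitted within a subgroup.

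Protocol 8.2.1 plans to assess consistency across demographic and clinical variables descriptively and by interaction tests.

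**The concern.** A categorical site effect is harmless when each site has several subjects in both arms. Within a subgroup, many sites may hold one or two completers, often all in the same arm. The site effect then absorbs them, and they carry no information on the treatment difference.

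The stake is the precision of the gender and race/ethnicity estimates and, in the smallest groups, whether there is an estimate at all. The SAP's purpose in 4.D is to check consistency of effect. A standard error (SE) well above the 4-point design effect cannot serve that purpose, and part of the imprecision comes from the choice of model and not from the number of subjects.

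**Working it through.** **Plan's own figure first.** SAP 7: "We have chosen to power our study to detect a four point effect", with a "standard deviation of 12.0 units for the change in total UPDRS from baseline" and two-sided alpha 0.05 at 80% power. Per group, 2 × (1.960 + 0.842)² × 12² / 4² = 141.3, so 142. Then 142 / 0.85 = 167.1, so 168, or 336 in all. This agrees with "making allowance for 15% dropouts the required sample size is 168 subjects per group". About 0.85 × 336 = 286 completers enter the primary analysis.

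**Strata.** About 56 sites (Protocol synopsis) less 8 pooled plus 1 super-site gives 49. The pooled sites hold 3+2+3+3+3+3+2+3 = 22 subjects, so the other 48 average (336 − 22) / 48 = 6.5 enrolled.

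**Information.** With a site effect, the information on treatment is the sum over strata of n1·n0/(n1+n0), and SE = 12 / √(information) before allowing for the baseline covariate. A site with one completer, or with two in the same arm, gives 0. A site with one in each arm gives 0.5.

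**Assumed inputs.**
- Share of women: 30-40%. The only figure in the documents is from the Phase II study, "There were 69 males, 30 females, predominantly White non-Hispanic", which is 30/99 = 30%.
- Minority share: 5-15%; the documents give none.
- Site sizes: at least 4 in each of the 48 sites, with even and skewed layouts.
- Randomization is blocked by site (Protocol 4.3.2.1). Block size is not given; 4 is assumed.
- Dropout 15% and SD 12, as in SAP 7. Subgroup membership is random across sites.

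**Women at 30%, by hand.** About 86 completers without a site factor give 86/4 = 21.5 units of information, so SE = 12/√21.5 = 2.6. In simulation the site strata keep 58-61% of this, or 12.5-13.1 units, so SE = 3.3-3.4.

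**Simulation, several hundred allocations per setting.** Uninformative means that all of the subgroup's completers in that stratum are in one arm. SEs use the design matrices of approaches (i) and (ii).

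| Subgroup share | Completers | Uninformative | SE (i) | SE (ii) | Variance ratio |
|---|---|---|---|---|---|
| Women 30% | 86 | 34-37% | 3.4-3.5 | 2.8 | 1.42-1.51 |
| Women 40% | 114 | 24-26% | 2.7 | 2.4 | 1.25-1.28 |
| Minority 15% | 43 | 57-63% | not listed | not listed | 2.3-2.5 |
| Minority 10% | 29 | 69-74% | 9.0-9.4 | 4.9-5.0 | 3.3-3.6 |
| Men 70% | 200 | 6.5% | 1.83 | 1.78 | (1.83/1.78)² = 1.06 |
| Non-minority 90% | not listed | 1.7% | 1.55 | 1.54 | (1.55/1.54)² = 1.01 |

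In the full trial 0.6% are uninformative and 95% of the information is kept.

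**Very small groups.** Residual degrees of freedom are completers − non-empty strata − 2. At a 5% share the averages are 14.3 − 12.3 − 2 = 0. No treatment estimate exists in 33-38% of runs, and there is no estimate or no residual degree of freedom in 69-75%. With about 6 completers (2% share) there is no estimate in 83-84%. At a 10% share it happens in only 1-3%.

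**Sensitivity.** Block size 2 gives 37% uninformative for women at 30% and 73% for a 10% group. With no dropout the figures are 29% and 67%.

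**Pooling redone inside the subgroup.** By the information formula, the SE for women at 30% falls from about 3.4 to about 2.65, and for a 10% group from about 8.5 to about 4.6. At 5% there is no estimate in 0.3% of runs.

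**The case against.** The strongest case on the other side is that approach (ii) is already planned, loses none of this information and matches Protocol 8.2.1, so only the source of the displayed estimates is in question. The analyses are exploratory, low power is conceded, and better SEs do not make them decisive. Power for 4 points in women rises only from about 22% (SE 3.4) to 30% (SE 2.8). In a 10% group it rises from about 7% to 13%, and the 95% half-width under (ii) is still 1.96 × 5.0 = 9.8 points. The separate refit also lets site effects, baseline slope and residual variance differ by subgroup, which is a fair reason to show it. The pooling rule might be read as applying afresh in each subgroup, and the SAP's planned test run on a simulated treatment code could expose a fit that fails.

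Much of this stands, and it limits the weight of the point. It does not remove it. SAP 4.D ties the separate subgroup results to (i) and never says that effects and intervals come from (ii). The clarification lists pooled sites by total enrolment, which tells against re-pooling. The concession on power concerns the number of subjects, whereas this loss comes on top and is avoidable.

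A reader might go further and infer that a third of women drop out of the analysis, that all 49 site effects persist in every subgroup, or that subgroup effects are generally not estimable. The documents do not support this. One third depends on a share borrowed from Phase II. Empty strata fall away, leaving about 40-42 among women at 30% and about 12 in a 5% group. Same-arm subjects sharing a site still inform the baseline slope and residual variance. Failure to estimate is a feature of very small groups. Nor is a model fit in each race/ethnic grouping certain, because the SAP says only that those results are tabulated separately.

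**Conclusion.** The point holds as a matter of efficiency in small subgroups. Followed as written, approach (i) raises the variance for women by about 25-50% relative to model (ii) and makes it about 2.3-3.6 times as large for a 10-15% minority group. In groups of about 14 completers or fewer it often gives no estimate or no test. The mechanism follows from the SAP's text. The sizes rest on assumed subgroup shares, site sizes and block size, and on membership being unrelated to site. Nothing here touches the primary analysis, and the larger subgroups lose little. It is worth changing because the remedy is cheap and the better model is already in the plan.

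**What to change.** In SAP 4.D, state that subgroup-specific treatment effects and confidence intervals are contrasts from the all-subject model in (ii), with site, baseline UPDRS, treatment, the characteristic and the interaction. If the separate refits in (i) are kept as a supplement, run them without the site factor, or reapply the fewer-than-four pooling to the subgroup's own counts.

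The cost is a sentence or two and no new data. Model (ii) assumes that site effects, the baseline slope and the residual variance are common to all subgroups. A refit without site gives up the site adjustment. Keeping such a refit beside (ii) gives a partial check on the common slope and variance.
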